## 9. DATA COLLECTION

### 9.1. PARTICIPANT REGISTRATION

Participants will be registered/enrolled for the trial at the time of consent and will be provided with a study ID.

### 9.2. FORMS AND PROCEDURE FOR COLLECTING DATA

All data will be collected on a paper Case Report File (see appendix) or recorded directly to an electronic CRF. Any paper CRFs will be de-identified and labelled with patient ID number and data will be transcribed to REDCAP database. The RedCap database will be accessible only by approved members of the research team. Once the study has concluded the PI will be the custodian of the database. All paper documents will be securely stored in a locked cabinet as per legal requirements. Paper documents will be destroyed 15 years post-study.

### 9.3. CASE REPORT FORMS AND SCHEDULE FOR COMPLETION

A case report form will be provided in the appendix. This study is completed following patient medical record assessment.

### 9.4. DATA FLOW

Protocol → CRF Design → Patient data collected in CRFs → Patient data in CRFs converted into raw data sets → Raw data sets → Create Tables/Listings/Figures → Create Analysis → Report

## 10. QUALITY CONTROL AND ASSURANCE

### 10.1. CONTROL OF DATA CONSISTENCY

All data will be collected by research staff (see CRF). Data will be collected on paper CRFs and de-identified using patient study IDs. All data will be transcribed to RedCap with permission to access only granted to study doctors and authorised research staff.

If feasible eCRFs will be used to ensure direct entry to improve efficiency and reduce entry errors, reduce data queries, missing data and maximise completed data.

## 10.2. PROTOCOL AMENDMENTS

All protocol amendments will be submitted to the HREC for approval prior to use. Trial sites will follow their local governance protocols to gain approval to commence this trial.

## 11. ETHICS

### 11.1. INVESTIGATOR AUTHORISATION PROCEDURE

Ethics and Governance approval will be obtained via the local HREC and governance offices prior to commencement of the study.

### 11.2. PATIENT PROTECTION

Research doctors and staff will ensure that the study is completed in accordance with the guidelines set out in the *National Statement on Ethical Conduct in Human Research* (2007) (the *National Statement*) and the *CPMP/ICH Note for Guidance on Good Clinical Practice* and any other relevant legislation/guidelines.

## 12. SAFETY

### 12.1. ADVERSE EVENT REPORTING

Adverse event

*The Australian Clinical Trial Handbook (The Handbook)* defines an adverse event (drugs) as:

any untoward medical occurrence in a patient or clinical investigation subject administered a pharmaceutical product and which does not necessarily have a causal relationship with this treatment. An adverse event can therefore be any unfavourable and unintended sign, symptom, or disease temporally associated with the use of a medicinal (investigational/experimental) product, whether or not related to this product.

Adverse drug reaction

*The Handbook* defines an adverse drug reaction as:

For unapproved medicines: all noxious and unintended responses to a medicinal product related to any dose should be considered ADVERSE DRUG REACTIONS. The phrase “responses to a medicinal product” means that a causal relationship between a medicinal product and an adverse event is at least a reasonable possibility.

---

 <http://www.tga.gov.au/industry/clinical-trials-handbook.htm> (definitions of adverse events are on 28-29).

For marketed medical products: a response to a drug which is noxious and unintended and which occurs normally used in man for prophylaxis, diagnosis or therapy of diseases or for modification of physical function.

Serious adverse event (SAE) or Serious Adverse Drug Reaction is defined as:

Any untoward medical occurrence that at any dose:

- results in death;
- is life-threatening, (NOTE: The term 'life-threatening' in the definition of 'serious' refers to an event in which the patient was at risk of death at the time of the event; it does not refer to an event/reaction which hypothetically might have caused death if it were more severe)
- requires in-patient hospitalisation or prolongation of existing hospitalisation;
- results in persistent or significant disability/incapacity;
- is a congenital anomaly/birth defect; or
- is a medically important event or reaction.

An adverse event or serious adverse reaction can also be any event or experience which compromises the ethical acceptability of the protocol. This can be a non-medical event for clinical trials that are not medical or testing drugs or devices, such as those clinical trials conducted in different fields such as psychology.

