## Summary

Study title:	Benefits of Analysing Brain Biomarkers in perinatal care: a prospective observational cohort study ( BABBIES Trial )
Protocol version	V 1, dated 29/05/2022
Objectives	
Primary objective	1) Provide feasibility data on the testing of umbilical cord blood for NfL and tau
Secondary objectives	

1) Provide a “normal range of plasma NfL and tau” associated with normal healthy deliveries

2) Provide preliminary data linking cord blood NfL and tau to adverse perinatal outcomes

3) Compare cord blood NfL and tau in elective caesarean deliveries to other deliveries involving a period of labour

4) Provide preliminary data linking cord blood NfL and tau to foetal developmental abnormalities

5) Provide preliminary data linking cord blood NfL and tau to abnormalities on intrapartum monitoring (CTG, scalp lactate)

6) Assess the impact of gestational age on plasma NfL and tau

7) Assess the impact of birth weight on plasma NfL and tau

8) Assess the impact of the duration of the 2nd stage of labour on plasma NfL and tau

9) Determine the proportion of consented patients in whom inadequate cord blood is not collected

Study design	Prospective observational cohort study
Planned sample size	110
Selection criteria	Caesarean deliveries and deliveries involving a period of labour
Study procedure	Umbilical artery and vein cord blood samples (3mL) will be obtained from births at RPAH by the midwife (when feasible)
Statistical considerations	A sample size of 92 placentae (24 elective caesareans, 68 laboured deliveries) is required to ensure that the value for the mean plasma NfL has a 95% confidence interval not exceeding 3pg/mL, with an added 20% (18 patients) to account for issues with biospecimen collection and storage and non-healthy deliveries.
Duration of the Study	6 months

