## 6.2. INVESTIGATION PLAN

### 6.2.1. METHODOLOGY

Interventions	Enrolment	Immediately post-delivery	2–4 weeks post-delivery
Participant Consent	✓		
Inclusion / Exclusion criteria	✓		
Adverse Event & Serious Adverse Event Assessment		✓	
Umbilical artery + vein blood sample collection		✓	
Patient medical record assessment			✓

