### 6.2.2 ADVERSE EVENTS/SERIOUS ADVERSE EVENTS

We anticipate no serious or non-serious adverse events with our study.

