## 6.3. STUDY PROCEDURE RISKS

There is a risk of blood exposure to the midwife collecting umbilical cord blood samples. This will be minimised by standard blood precautions including the use of personal protective equipment. There is a possibility of damage to placenta in the process of collecting umbilical cord blood samples, which may interfere with placental histopathology, if it is indicated. The overall risk of this is very low. Both of the aforementioned risks of our study are offset by the fact that cord blood sampling is taken as standard of care in all patients giving birth at RPA—we will only be adding to the amount of blood taken, rather than affecting the decision of whether blood should be taken or not. The extra 3mL of blood obtained as part of this study is unlikely to represent any meaningful increase in the baseline risks of cord blood sampling described above. Blood will be taken for rhesus and cord gas analysis as a priority, and we will only assess blood that is provided in surplus of these requirements. We will not use cord blood that is otherwise required for essential investigations at the time of birth. As such, research activities will not disrupt any standard care.

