## 12.2. SERIOUS ADVERSE EVENT REPORTING

All serious adverse events will be reported immediately to the sponsor and the HREC. The reports will be followed by a detailed written report. Follow-up reports will identify the participant/s by unique code assigned to participants (rather than by name).

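### The safety section uses drug-trial definitions that do not fit a cord-blood sampling study, so sampling harms are not reliably captured and the serious-event rule overlaps the study's own outcomes

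*Protocol*

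**What the plan says.** The Protocol describes a "prospective observational cohort study" in which midwives collect an extra 3 mL of cord blood. It administers no product.

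- **Named risks (6.3).** "There is a risk of blood exposure to the midwife collecting umbilical cord blood samples". There is also a "possibility of damage to placenta in the process of collecting umbilical cord blood samples, which may interfere with placental histopathology". The section adds that rhesus and cord-gas blood is taken first and that standard care will not be disrupted.
- **Expectation (6.2.2).** "We anticipate no serious or non-serious adverse events with our study".
- **Adverse-event definition (12.1).** "any untoward medical occurrence in a patient or clinical investigation subject administered a pharmaceutical product", followed by definitions of adverse drug reactions. A closing clause widens the term to events that undermine the ethical acceptability of the protocol, including non-medical ones.
- **Serious events (12.1).** The stem refers to dose. The list includes death, congenital anomaly and an event that "requires in-patient hospitalisation or prolongation of existing hospitalisation". No relation to a study procedure is required.
- **Reporting (12.2).** "All serious adverse events will be reported immediately to the sponsor and the HREC". Nothing is exempted.
- **Schedule (6.2.1).** "Adverse Event & Serious Adverse Event Assessment" is ticked once, immediately after delivery, in the same column as cord sampling. The record review at 2–4 weeks has no such tick.
- **Outcomes (7.1).** Special-care or intensive-care admission, readmission within two weeks, perinatal death and serious congenital abnormality all make a delivery non-healthy.

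**The concern.** A safety definition should identify the harms that the study procedure could cause and separate them from the clinical events under study. Section 12.1 does neither well. Its main definition depends on an exposure that never occurs here, so the harms the protocol itself foresees fall outside it. Its serious-event list describes events expected in any birth cohort whether or not extra blood is taken.

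The study's primary objective is feasibility (3.1), ahead of a district-wide cohort (1.2). Whether added sampling exposes collectors, damages placentae or displaces a standard-care sample bears on planning that cohort. If 12.1 and 12.2 are followed literally, staff must decide case by case what counts, in whom and until when. Two people applying the same text could produce quite different safety records.

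**Working it through.** The documents give no adverse-event count or rate, so there is no figure to reproduce. The check compares the sections with one another.

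**Step 1. Do the foreseeable sampling harms meet the stated rules?**

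| Event | Main definition (12.1) | Closing clause (12.1) | Within the one assessment (6.2.1) | Case report form (section 17) |
|---|---|---|---|---|
| Collector blood exposure | No: not a subject, no product | Arguable | Yes | No item |
| Placental damage from sampling | No: no product | Arguable | Yes | No dedicated item; free text under placental abnormalities or complications |
| Requested histopathology compromised | No: no product | Arguable | No: shows later | No item |
| Rhesus sample insufficient | No: no product | Arguable | Yes | No item |
| Cord-gas sample missed | No: no product | Arguable | Yes | Indirect: blank gas fields |

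The closing clause asks whether ethical acceptability is compromised, and its example is a non-medical field. A single blood exposure or one torn placenta does not plainly meet that test. Section 12.2 also identifies people in follow-up reports by participant code, which a midwife does not have.

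**Step 2. Do the study outcomes meet the serious-event list?** Set the reference to dose aside, since otherwise the list could be read as excluding everything. Perinatal death and congenital anomaly then match directly. Readmission is hospitalisation. Special-care or intensive-care admission meets the hospitalisation criterion at least where the stay is prolonged. Section 12.2 makes all of these immediately reportable.

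**Step 3. In whom?** Section 6.7 takes consent from the person giving birth. No section says whether the neonate is a subject for safety reporting. Excluding neonates does not remove the overlap: the form records maternal events such as post-partum haemorrhage, uterine rupture and puerperal sepsis, and any that prolongs her stay meets the list.

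**Step 4. Size, for illustration.** Take N = 110 (4.2) and let p be the share of births with at least one neonatal outcome on the serious-event list. The documents give no value of p, so it is an assumption. Expected number = 110 × p; chance of at least one = 1 − (1 − p)^110.

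- p = 2%: 110 × 0.02 = 2.2; 1 − 0.98^110 = 0.89
- p = 5%: 110 × 0.05 = 5.5; 1 − 0.95^110 = 0.997
- p = 10%: 110 × 0.10 = 11; chance about 1.00
- p = 20%: 110 × 0.20 = 22; chance about 1.00

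If neonates count, the expectation in 6.2.2 is unlikely to hold under the literal list anywhere in this range.

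**Step 5. Window.** Readmission is defined over two weeks after birth, so it always falls after the only assessment. The 2–4 week record review would find it, but safety assessment is not scheduled there.

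**The case against.** The best defence is that 12.1 does not stop at the drug definition. Its closing clause could admit a sampling incident, particularly one that broke the undertaking on standard care. This stands in part. A reader might infer that the protocol cannot capture any sampling harm, but the clause rules that out. Capture is unreliable rather than impossible.

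A reader might also infer that the assessment is at the wrong time for the named risks. It is not: exposure and placental damage arise at sampling, in the same schedule column. The timing gap concerns later consequences and readmissions.

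The form is not wholly silent. It has cord-gas fields and free-text entries where placental damage might be written, and 6.1 requires inadequate study samples to be recorded. Taking standard-care blood first also limits the risk of disruption by design. These points stand, but none gives a dedicated record of exposure, sampling damage or rhesus-sample adequacy.

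It is tempting to predict that unrelated reports would swamp oversight and leave the safety record uninformative on every reading. The documents do not support that. The number depends on an assumed rate and on neonates counting as subjects. Even 11 to 22 reports over the six-month study is about 2 to 4 a month (11/6 = 1.8; 22/6 = 3.7). Section 12.2 names the sponsor and the HREC, not the monitoring board, as recipients.

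Finally, 6.2.2 can be read as expecting no events caused by the study. That is sensible, but neither 12.1 nor 12.2 limits events in that way. Safety is not an objective or endpoint, so no estimate changes.

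**Conclusion.** The point holds as a mismatch between the safety rules and the study. The main adverse-event definition rests on a product the study does not give, so the risks named in 6.3 are caught only, if at all, by a vague clause and have no dedicated item on the form. The serious-event list and the immediate-reporting rule overlap the 7.1 outcomes with no relatedness condition or exemption, and this sits badly with 6.2.2. The status of the neonate is unstated, and readmissions and late histopathology effects fall after the only assessment.

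The size can only be illustrated: 2.2 to 22 reportable births out of 110, assuming a 2% to 20% rate and that neonates count as subjects. The textual conflict depends on neither assumption. Sample size and the biomarker analyses are unaffected. The protocol should be amended, because the problem is a stated rule that does not fit the study rather than a missing detail.

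**What to change.** 1. In 12.1, replace the drug definitions with one tied to the sampling procedure: blood exposure of the collector; placental or cord damage from sampling; rhesus or cord-gas sample missed or insufficient; requested placental histopathology compromised.
2. Add these four as yes/no items on the case report form.
3. In 6.2.1, tick adverse-event assessment at the 2–4 week record review as well as immediately after delivery.
4. Reconcile 6.2.1, 6.2.2, 7.1, 12.1 and 12.2. State in whom events count (person giving birth, neonate, collector). State that 7.1 outcomes are recorded as study outcomes, with expedited reporting when judged related to sampling.

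The cost is protocol wording, one schedule tick and four tick-boxes. The information comes from the collecting midwife and the record review already planned. The downside is slightly more form completion.

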## 12.2. SERIOUS ADVERSE EVENT REPORTING

All serious adverse events will be reported immediately to the sponsor and the HREC. The reports will be followed by a detailed written report. Follow-up reports will identify the participant/s by unique code assigned to participants (rather than by name).

## 12.3. DATA SAFETY AND MONITORING BOARD (DSMB)

A DSMB comprising of independent experts will be assigned prior to trial commencement.

## 12.4. EARLY TERMINATION

If early termination of the research project is required the Principal Investigator [name] will communicate with the HREC and Governance offices. All policies and procedures will be followed and documented.

## 13. BLINDING AND UNBLINDING

There will be no blinding as part of this study.

---

 Ibid.

 Ibid.

#### 14. CONFIDENTIALITY AND STORAGE AND ARCHIVING OF STUDY

Electronic data will be stored in a secured online database (RedCAP) only accessible to those with authorised access to the data for analysis purposes. Any staff who no longer require access to the online data will be removed from the database.

Paper CRFs will be kept in a locked secure file cabinet within the locked Department of Anaesthetics and keys will be kept in a safe location for those who require access. All documents will be held for 15 years as per legal requirements.

#### 15. TRIAL SPONSORSHIP AND FINANCING

This trial is being supported by the Department of Anaesthesia, Royal Prince Alfred Hospital.

## 17. APPENDICES

Data Collection Sheet/CRF

BABBIES Case Report File

**Demographics**

**Date of Admission:** \_\_\_\_\_ **Date of Birth:** \_\_\_\_\_

Factor	Outcomes
--------	----------

DOB (Age)	____ / ____ / ____    ____ years old
Weight	_____ kg
Height	_____ cm
Ethnicity	OCEANIAN NORTH-WEST EUROPEAN SOUTHERN AND EASTERN EUROPEAN NORTH AFRICAN AND MIDDLE EASTERN SOUTH-EAST ASIAN NORTH-EAST ASIAN SOUTHERN AND CENTRAL ASIAN PEOPLES OF THE AMERICAS SUB-SAHARAN AFRICAN
Indigenous	Aboriginal Torres Strait Islander Aboriginal and Torres Strait Islander Unknown Prefer not to say
Medications (Name/Dose)	
Diabetes	Type 1 diabetes Type 2 diabetes Gestational diabetes None Unknown
Multiple pregnancy	MCMA MCDA DCDA No Unknown
Alloimmunisation prophylaxis (28 + 36 weeks)	Required: yes/no Given:    yes/no

	Unknown
Hypertensive Disorder	Gestational hypertension Chronic hypertension None Pre-existing
Previous miscarriage/loss of pregnancy	
Alcohol	Yes/No/Unknown  Quantity (drinks/week) _____
Tobacco	Yes/No/Unknown  Smokes/week _____
Other drug use	Yes/No/Unknown  Type/Amount _____
Folate supplementation	Taken regularly Taken irregularly Not taken Unknown
Maternal health issues	Cardiovascular disease Thrombophilia Autoimmune disease Inflammatory Bowel Disease Asthma Obesity Malignancy Neurological disease (Description: _____) Other (Description: _____)
Number of previous births and Route of Delivery	

**Prenatal screening**

Factor	Outcome
Group B Streptococcus status	Positive Negative Not done Unknown
Prenatal fetal screening tests	1 st trimester combined screening 2 nd trimester combined screening NIPT None Unknown  Results:
Prenatal ultrasounds	Abnormal (Description: _____) Normal Not done Unknown
Screened infections	HIV (positive/negative) HBV (positive/negative) HCV (positive/negative) Syphilis (positive/negative) Rubella (positive/negative) Varicella (positive/negative) None Not done Unknown
Other infections	Yes/No/Unknown  1. Description: _____
Maternal iron deficiency	Yes/No/Not done/Unknown  2. Ferritin (lowest): _____ ug/L

Maternal anaemia	Yes/No/Not done/Unknown 3. Haemoglobin (lowest): _____ mg/L
Midstream urine test	Asymptomatic bacteriuria UTI Normal Not done Unknown

### Antenatal complications

Factor	Outcome
Hyperemesis gravidarum	Yes/No/Unknown
Pre-eclampsia	Pre-eclampsia Eclampsia HELLP syndrome None Unknown
Placental abruption	Yes/No/Unknown  Notes:
Sepsis	Yes/No/Unknown  Notes:
Placental abnormalities at birth	Subchorionic haematoma Placenta praevia Vasa praevia Single umbilical artery Velamentous cord insertion Circumvallate Other (Description: _____) None Unknown

Maternal embolism	Thromboembolism Air embolism Amniotic fluid embolism None Unknown
Polyhydramnios	Yes/No/Unknown
Oligohydramnios	Yes/No/Unknown
Antepartum haemorrhage	Yes/No/Unknown  Notes:
Intrauterine growth restriction	Small for gestational age Fetal growth restriction None Unknown
Twin-to-twin transfusion syndrome	Present Absent Not applicable Unknown

### **Intrapartum factors**

Factor	Outcomes
Prelabour rupture of membranes	PROM PROM >24 hours from birth None Not applicable Unknown
Preterm Birth (<37 weeks)	Yes/No/Unknown
Induction of labour	Required Not required Unknown  Notes: (AROM, cervical ripening methods, etc.)

Duration of 1st stage of labour	4. _____ hours/not applicable
Duration of 2nd stage of labour	5. _____ hours/not applicable
Fetal presentation	Cephalic Breech Transverse Oblique Unstable Unknown Fundic/cord presentation
Fetal distress	Yes/No/Unknown  Notes:
Fetal lactate sample + result	Sampled/not sampled/unknown  _____ mmol/L
Cardiotocography abnormalities	Present (Description: _____) Absent Not applicable Unknown
Pain management	Epidural Nitrous oxide Pethidine Other (Description: _____) None Unknown
Anaesthetic complications	Yes/No/Unknown  6. Description: _____
Caesarean section delivery	Category 1 – Reason: Category 2 Category 3

	Category 4 Not applicable Unknown
Uterotonic agent administration	Oxytocin (units) _____ Ergometrine (mg) _____ Syntometrine (units, mg) _____ Misoprostol (mcg) _____ Carboprost (mcg) _____ Carbetocin _____
Post-partum haemorrhage	Yes/no/unknown (text description)
Umbilical cord gas	pH: Base excess: pCO 2 : PO 2 :
Blood loss	_____ mL
Complications	Uterine rupture Umbilical cord prolapse Chorioamnionitis Puerperal sepsis Other (Description: _____) None Unknown

### Neonatal factors

Factor	Outcomes
Birth weight	_____ kg
Gestational age at birth	_____ weeks _____ days
Preterm birth	Spontaneous Iatrogenic Not applicable Unknown
Postnatal death (first two weeks)	Yes/No/Unknown  Notes:

Injuries from birth	Cephalohaematoma Subgaleal haemorrhage Caput succedaneum Erbs Palsy Clavicle /humeral fracture Cranial nerve palsy Laceration Facial Bruising Other (Description: _____) None Unknown
Neonatal ICU admission	Yes/No/unknown Duration of Stay: _____ days
Special care nursery admission	Yes/No/unknown Duration of Stay: _____ days
Resuscitation at birth	Yes/No/unknown  Notes:
APGAR score at 1 minute	_____ (0–10)
APGAR score at 5 minutes	_____ (0–10)
Vaccinations	Yes/No/Unknown Description: _____
Resuscitation at any point in admission	Yes/No/unknown Description and Outcome: _____
TORCH infections	Toxoplasma (Yes/No) Rubella (Yes/No) Cytomegalovirus (Yes/No) HIV (Yes/No) Hepatitis viruses (Yes/No) Herpes simplex virus (Yes/No) Parvovirus B19 (Yes/No) Syphilis (Yes/No)

	
Varicella zoster virus (Yes/No)
 
None
 
Unknown

Genetic disorders	
Trisomy 21
 
Trisomy 18, 14, or 13
 
Klinefelter syndrome
 
Turner syndrome
 
Spinal muscular atrophy
 
Fragile X syndrome
 
Cystic fibrosis
 
Other (Description: _____)
 
None
 
Unknown

Birth defects	
Congenital heart disease
 
Neural tube defects (Description: _____)
 
Abdominal wall defects
 
Congenital diaphragmatic hernia
 
Tracheal abnormalities
 
Oesophageal atresia
 
Pulmonary hypoplasia
 
Other (Description: _____)
 
None
 
Unknown

Neonatal sepsis	
Early onset sepsis
 
Late onset sepsis
 
None
 
Unknown

Metabolic complications	
Hypoglycaemia
 
Hypothermia
 
Anaemia
 
Polycythaemia
 
Congenital hypothyroidism

	
Metabolic bone disease of prematurity
 
Haemolytic disease of the newborn
 
Congenital adrenal hyperplasia
 
Other (Description: _____)
 
None
 
Unknown

7. Neonatal jaundice	
8. Present/Absent/Unknown
 
9. Peak serum bilirubin level: _____umol/L
 
10. Direct antibody test: Positive/Negative/Not done
 
11. Suspected cause: _____

Gastrointestinal complications	
Necrotising enterocolitis
 
Biliary atresia
 
Neonatal hepatitis
 
Other (Description: _____)
 
None
 
Unknown

Respiratory complications	
Respiratory distress syndrome
 
Apnoea of prematurity
 
Bronchopulmonary dysplasia
 
Transient tachypnoea of the newborn
 
Pneumothorax
 
Pneumonia
 
Meconium aspiration syndrome
 
Persistent pulmonary hypertension of the newborn
 
Other (Description: _____)
 
None
 
Unknown

Neurological complications	
Cerebral palsy
 
Intraventricular haemorrhage
 
Retinopathy of prematurity
 
Hypoxic–ischaemia encephalopathy
 
Periventricular leukomalacia

	
Seizures
 
Movement disorders
 
Other (Description: _____)
 
None
 
Unknown

Haematological complications	
Anaemia of prematurity
 
Physiological anaemia of the newborn
 
Other (Description: _____)
 
None
 
Unknown

Readmission to hospital in 2 weeks following birth	
Yes/No/Unknown
 
Description/length of stay:

